# 5.3 Drug Accountability

The investigator will maintain adequate records of the disposition of the darTreg products and Thymoglobulin®, including the date, lot ID, and dose of the product, dose received, name of the recipient (participant-by-participant accounting), and a detailed accounting of any product that is accidentally or deliberately destroyed. Used vials of Thymoglobulin will be maintained on site until drug reconciliation. No Thymoglobulin vial may be destroyed without the expressed approval of study sponsor.

Records for receipt, storage, use, and disposition will be maintained by the study site. A dispensing log will be kept current for each participant. All records regarding the disposition of the investigational product will be available for inspection.

# 5.4 Toxicity Prevention and Management (Dose Escalation Plan)

#### 5.4.1 Overview

Eligible patients will receive either no darTreg infusion (a total of 6 subjects, 3 at each clinical site; Cohorts 1a and 1b) or a single infusion of darTregs at one of 3 dose levels: 50, 200, and 800 million (Cohorts 2, 3, and 4). Three patients will be planned for each darTreg dose, with the possibility of expanding to 6 patients for Cohorts 2 and 3 as required; the last dosing group will have 6 patients.

Progression from one group to the next will be based on the cumulative frequency and severity of specific AEs as described in 14.8.

Confidential Page 39 of 80

#### 5.4.2 Enrollment Pace and Dynamics

#### 5.4.2.1. Cohort 1

Subject enrollment will take place in a staggered fashion (Figure 11. Staggered Enrollment). Center 1 will enroll the first group of 3 participants (Cohort 1a) that will receive Thymoglobulin®+EVR IS but will not receive darTregs. Upon completion of enrollment and at least 12 weeks of observation for the last participant in Cohort 1a, and in the absence of any safety signals, enrollment will proceed in Cohort 2 (darTreg Dose A). Enrollment into Cohort 2 from participating centers will not begin until enrollment in cohort 1b is complete.

### 5.4.2.2. Cohorts 2, 3, and 4

For Cohorts 2, 3, and 4 that will receive escalating darTreg doses, the first subject at each dose will be monitored for 4 weeks after darTreg infusion to ensure that there are no safety signals (Section 14.8). Subsequently, a 4-week observation period between darTreg infusions for the second and third subjects in the same cohort and between the last subject in one cohort and the first darTreg infusion in the next cohort is recommended but not mandatory. If the expected time interval between darTreg infusions is less than two weeks, the PI and NIAID medical monitor will review the status of the study and determine whether Thymoglobulin® should be initiated, Progression from one cohort to the next will depend on the cumulative incidence of sentinel AEs as described in Section 14.8.

[figure not shown]

Figure 11. Staggered Enrollment

# **5.4.3** Rationale for Staggering Intervals

All participants in Cohort 1a – those who receive Treg supportive IS alone - must be monitored for 12 weeks prior to enrollment of Cohort 2 and Cohort 1B by the second clinical site. The rationale for selecting 12 weeks is that this interval covers the time period that has the highest incidence of important post-liver transplant complications such as rejection and infection, particularly bacterial and fungal infections related to the transplant operation including those directly related to the transplant incision / wound.

Within each darTreg dosing cohort, there is a mandatory four-week observation period after the administration of darTregs to the 1st patient of each cohort before the 2nd patient can receive darTregs. We have selected a shorter observation time interval for several reasons. First, darTregs will be administered sometime between Week 11-20 after transplant. This is a period of relative clinical quiescence that will readily permit optimal identification of AEs that may be precipitated by the darTreg infusion. Liver transplant recipients have largely recovered from the transplant operation as well as from the baseline liver disease. They continue on anti-viral (until 6 months after transplantation) and anti-

Confidential Page 40 of 80

pneumocystis prophylaxis (until at least 12 months after transplantation) such that the frequency of these infections is very low. Second, we anticipate that the majority of complications associated with darTreg administration (infusion reaction, AR, or infection) are most likely to occur early, soon after administration while the beneficial effect of darTreg administration may well evolve and/or intensify over time. Infection may be precipitated by contamination of the darTreg preparation with infectious agents or with non-donor-alloantigen-reactive Tregs that lead to generalized over-immunosuppression. Similarly, rejection may be precipitated by contamination of the darTreg preparation with T effector cells. In these cases, the deleterious impact of darTreg infusion is expected to manifest soon – within 4 weeks – after infusion. While malignant transformation of infused cells is a concern, the timeframe of this complication as well as its manner of presentation is certainly difficult if not impossible to predict and therefore, this safety concern cannot be mitigated by any sort of mandatory waiting period.

## 5.4.4 Management Plan for Out of Range darTreg Doses

For subjects in cohort 2, any product with less than 25 million darTregs will not be infused and subject will be replaced. In cohort 3, products falling short of defined dose range for the cohort will be infused up to maximum of range for cohort 2 in up to 2 subjects, with the subject(s) contributing to cohort 2. The UCSF HICTF, NIAID MM, and study PI will review available information after the first instance of the dose falling short of target range, and again in the event of a second product not meeting the specified dose. One subject will be allowed to receive study directed Thymoglobulin under circumstances described. Recruitment and enrollment activities can continue during this time. If a third instance of lower-than-expected dose is manufactured, the study will be paused and DSMB will review available data prior to the trial proceeding.

If a higher dose of darTregs is produced than specified for a cohort, the maximum defined dose for that cohort will be packaged in the product and infused. Cells not infused will be used for research.

[figure not shown]
Table 2. RTB-002/delta Dose Ranges

	Target Dose for Cohort	Dose Range
Cohort 2	50 million cells	25-60 million cells
Cohort 3	200 million cells	100-240 million cells
Cohort 4	800 million cells	400-960 million cells

Figure 12. Algorithm for Out of Range darTreg Doses

# Algorithm for Out of Range darTreg Doses

# If number of darTregs manufactured is:

Confidential Page 41 of 80

#### 6. Other Medications

# **6.1** Immunosuppressive Medications

# 6.1.1 Zortress® (Everolimus)

For this study, EVR will be used in combination with TAC following taper and cessation of corticosteroids (Figure 9. EVR-based Regimen after Thymoglobulin®). The suggested starting dose for this trial is 1.0-1.5 mg bid since our target trough level is 6 to 8  $\mu$ g/mL. This is based on data from the de novo liver transplant EVR trial. Participants who had a trough level of 6-8  $\mu$ g/mL required a mean (median, standard deviation) daily dose of 4.4 (4.0, 1.75) mg. Subjects meeting eligibility criteria for EVR conversion (Screen C2) will begin EVR no sooner than 30 days after liver transplantation and no later than 44 days after transplantation; with target trough levels of 6-8  $\mu$ g/L. EVR target trough levels will be further reduced to 4-6  $\mu$ g/L 24 – 26 weeks after transplantation.

#### 6.1.2 Tacrolimus

Tacrolimus will be initiated within 72 hours of liver transplantation, targeting 12 hour trough levels of 6-8  $\mu$ g/L. At 5-6 weeks after transplantation, after EVR is initiated in eligible subjects, the TAC target 12 hour trough levels will be decreased to 3-5  $\mu$ g/L (Figure 9. EVR-based Regimen after Thymoglobulin®). Subjects ineligible for EVR conversion will remain on TAC with target levels of 3-8  $\mu$ g/L with MMF (Figure 10. TAC-based Regimen after Thymoglobulin®).

Inability to tolerate TAC leading to discontinuation or conversion to cyclosporine will result in early termination from the clinical trial and reversion to standard of care IS.

#### 6.1.3 MMF

MMF will be initiated within 24 hours of transplantation. If Cellcept is used, then the dosing will be 500 mg twice daily intravenously or by mouth. If Myfortic is used, then the dosing should be 360 mg twice daily by mouth. For subjects who convert to EVR, MMF must be discontinued as soon as target EVR trough levels have been achieved. Subjects ineligible for EVR conversion will remain on Cellcept or Myfortic.

#### 6.1.4 Prednisone

Solumedrol 500 mg will be given intravenously on the day of transplantation. Additional Solumedrol will be prescribed according to center standard of care. Oral prednisone should be initiated once oral medication is tolerated. Steroid doses may be further tapered on an individualized basis depending on the clinical status of patient and function of graft. Corticosteroids must be discontinued by day 44 after transplant. For subjects eligible for EVR, corticosteroids must be discontinued prior to initiating EVR.

#### **6.1.5** Other permitted concomitant medications

Other non-immunosuppressive concomitant medications used as standard of care in the management of the liver transplant subject (e.g. cholesterol lowering medications, blood pressure lowering medications, etc.) not specifically described in *Section 6.3. Prohibited Medications* are acceptable in the study.

#### 6.2 Prophylactic Medications

#### 6.2.1 Recommended Pre-Medications for Thymoglobulin®

Solumedrol 500 mg IV is recommended prior to first dose of Thymoglobulin®; and Solumedrol 250 mg IV prior to the second dose of Thymoglobulin®. Corticosteroid dosing prior to subsequent doses of Thymoglobulin® will be at the site investigator's discretion. Acetaminophen 500 mg PO and diphenhydramine 50 mg IV 1 hour prior to first and second doses of Thymoglobulin® is also recommended. At the site investigator's discretion, acetaminophen and diphenhydramine can be continued every 6 hours around the clock to cover the timeframe of the first two infusions.

Confidential Page 42 of 80

### 6.2.2 Pre-Medications for darTreg Infusion

Pre-medications will be administered 30-60 minutes prior to the darTreg infusion. Pre-medications will include 650 mg acetaminophen and 25-50mg diphenhydramine intravenously or by mouth.

#### 6.2.3 Anti-Infective Prophylaxis Post-Transplantation

Intravenous gancyclovir and/or oral Valcyte will be administered for the prophylaxis of CMV and EBV for at least six months after liver transplantation. Participants should receive center standard of care prophylaxis for candida infection until discontinuation of corticosteroids and pneumocystis infection for the duration of the study.

#### 6.3 Vaccinations

Subjects should receive seasonal influenza vaccinations as SOC. However, subjects should not receive any vaccination within 28 days prior to blood collection for darTreg manufacturing and/or within 14 days prior to the actual infusion (see Schedule of Events and darTreg exclusion criteria). In addition, the subjects should not have any vaccination for 28 days after the date of darTreg infusion. These requirements are in place to minimize the chance of having enrichment of influenza-reactive Tregs in the product and ensure that Treg infusion does not negatively impact influenza immunity elicited by the vaccine.

#### 6.4 Prohibited Medications

Cyclosporine cannot be used as an alternative to tacrolimus in this trial. The indication for use of EVR in liver transplantation for the primary prophylaxis of AR is in combination with tacrolimus.

IS medications other than those specified in the protocol are similarly disallowed. These include, but are not limited to azathioprine, basiliximab, alemtuzumab, sirolimus, rituximab, intravenous immune globulin, and belatacept.

The use of live vaccines will be proscribed during the follow up period, as per standard of care for liver transplant recipients. Examples include (but are not limited to) the following: intranasal influenza, measles, mumps, rubella, oral polio, BCG, yellow fever, varicella, and TY21a typhoid vaccines.

Grapefruit and grapefruit juice inhibit cytochrome P450 3A4 and P-gp activity and should therefore be avoided with concomitant use of EVR. Patients with rare hereditary problems of galactose intolerance, the Lapp lactase deficiency or glucose-galactose mal absorption should not take EVR as this may result in diarrhea and malabsorption.

Administration of medications known to interact with tacrolimus and/or EVR is allowed but tacrolimus and EVR levels should be carefully monitored and dosing titrated to maintain the target levels to minimize toxicity while maintaining efficacy.

Confidential Page 43 of 80

### 7. Premature Discontinuation of Investigational Therapy

# 7.1 Premature Discontinuation of Thymoglobulin and/or Treg Supportive IS Regimen

Study IS regimen may be prematurely discontinued for any participant for any of the following reasons:

- 1. Inability to tolerate at least 3 mg/kg Thymoglobulin® or inability to deplete CD3 count to less than or equal to 50μ/L (50/mcL) or total lymphocyte count to less than equal to 0.1 x 109/L after study Thymoglobulin® administration
- 2. Inability to tolerate TAC- or EVR-based maintenance IS
- 3. The diagnosis of severe AR (Banff criteria) at any time after transplantation
- 4. The diagnosis of early or late CR (Banff criteria) at any time after transplantation
- 5. The occurrence of steroid refractory rejection at any time after transplantation
- 6. Poor compliance with study procedures.
- 7. Investigator decision that the study IS regimen and/or future study treatment is no longer in the best interest of the participant.
- 8. Failure to manufacture and supply the cellular product two times for the same subject

There are a myriad of diagnoses that might lead an investigator to determine that the study IS regimen and/or darTreg infusion is no longer in the best interest of the participant. While there are likely an infinite number of specific reasons, general reasons include severe, life-threatening infections, malignancy (excluding skin cancer), GvHD, pneumonitis, severe renal dysfunction / proteinuria, serious medical co-morbidity such as myocardial infarction, and logistical issues including patient relocation and record of non-compliance.

The (Data Safety Monitoring Board) DSMB will be provided with information about cases of premature discontinuation occurring in any stage. Subjects who have prematurely discontinued the study regimen will enter into a schedule of events (SOE) of reduced monitoring intensity for purpose of safety (Please refer to Section 13.4 and Safety Follow-Up SOE)

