# Treatment Description

#### Treg-supportive IS regimen:

- Rabbit anti-thymocyte globulin (Thymoglobulin®) induction (3-4.5 mg/kg started by day 3)
- Corticosteroids (500 mg intra-operatively, taper to off by week 5)
- Mycophenolate mofetil (1000 mg total daily dose)
- TAC, with target trough level of 6-8 μg/dL

Between 30 and 44 days following transplant: Subjects who are not eliminated by Exclusion Criteria C1 (Section 4.3.3) will proceed in the study and receive either TAC-based or EVR-based IS, based on eligibility Criteria C2 (Section 4.3.4)

- TAC-based IS: reduce TAC trough level to 3-8 μg/dL; continue MMF
- EVR-based IS: reduce TAC trough level to 3-5 μg/dL; EVR target trough level of 6-8 μg/dL; decrease then discontinue MMF

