This trial importantly enrolls subjects undergoing deceased donor liver transplantation. As a consequence of increased cold ischemia time and reduced donor quality that results in substantial ischemia / reperfusion injury, a significant proportion of deceased donor liver recipients incur severe acute kidney injury in the immediate peri-transplant timeframe. Since trajectory of renal recovery is unpredictable, use of mTOR might not be appropriate because of low GFR and/or proteinuria. These subjects will be maintained on a regimen of TAC and MMF, albeit at TAC trough levels and MMF doses lower than standard of care to optimize renal function. We believe that this will be sufficient IS to prevent rejection since they have received thymoglobulin, which depletes T cells for months. Finally, it is also possible that subjects who successfully convert to EVR-based IS may experience toxicities that mandate EVR discontinuation concomitant with reinitiation of MMF. In light of the results of the recent Japanese trial, allowing darTreg administration in subjects maintained on either TAC-EVR or TAC-MMF IS is a justifiable approach. Obtaining safety and mechanistic data from subjects on either IS regimen in the context of darTreg administration will be valuable in proceeding with subsequent efficacy trials.

[figure not shown]

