#### 4.3.3 Exclusion Criteria C1

Below are exclusion criteria to be assessed at day 30-44 after transplantation for continuation in the trial. All subjects regardless of eligibility for EVR conversion, with any of the following will not receive darTregs and will move into safety follow up.

- 1. Explanted liver with evidence of increased risk of recurrent cancer (HCC tumor burden exceeding the Milan criteria; presence of vascular invasion; cholangiocarcinoma morphology)
- 2. Insufficient depletion of recipient T cells, defined as a nadir CD3 count ≥50 cells/µL (50 cells/mcL) or total lymphocyte count ≥ 0.1 x 10^9/L if CD3 count is unavailable
- 3. Development of a condition requiring chronic anti-coagulation
- 4. Clinical evidence of untreated biliary obstruction
- 5. ALT >2.0 x upper limit of normal (ULN)
- 6. Inability to taper off corticosteroids by 44 days (+/- 2 days) after transplant
- 7. Detectable circulating HCV

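### Trough-target units and steroid-stop deadlines differ between sections, and no operational section says what follows everolimus intolerance

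*Protocol*

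**What the plan says.** **Trough targets.** The synopsis treatment description states "TAC, with target trough level of 6-8" in μg/dL. It uses the same unit for the later tacrolimus (TAC) targets (3-8 on the TAC-based regimen, 3-5 with everolimus) and for everolimus (EVR, 6-8). Section 6.1.1 gives the EVR target of 6-8 first in μg/mL and later in the same paragraph in μg/L. Sections 1.2.3, 6.1.2 and 10.2, the appendices, and criteria D7 and D8 use μg/L. D7 excludes a subject from infusion if the TAC trough is above 8 μg/L.

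**Steroid stop.** The synopsis says "taper to off by week 5", and Appendix 1 also gives week 5. Section 6.1.4 sets day 44. Criterion C1 item 6 excludes for "Inability to taper off corticosteroids by 44 days (+/- 2 days) after transplant". Section 6.1.4 adds: "For subjects eligible for EVR, corticosteroids must be discontinued prior to initiating EVR". Section 6.1.1 has EVR starting no sooner than day 30 and "no later than 44 days after transplantation".

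**EVR intolerance.** Section 1.2.4 recognises that converted subjects "may experience toxicities that mandate EVR discontinuation concomitant with reinitiation of MMF", and it supports darTreg infusion on either TAC-EVR or TAC-MMF. Section 7.1 opens with "Study IS regimen may be prematurely discontinued for any participant for any of the following reasons" and lists as item 2 "Inability to tolerate TAC- or EVR-based maintenance IS". Subjects who discontinue the regimen move to a schedule with less intensive monitoring.

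**The concern.** Sites act on these figures. A trough target whose unit changes between sections is a drug-level instruction that cannot be right everywhere as printed, and it sits beside an infusion criterion defined on the same measurement.

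The steroid dates matter because they interact with the EVR start window. The latest steroid stop that C1 tolerates falls after the last permitted EVR start, so a subject can stay in the trial without the text saying which regimen applies. Section 3.3 sets out to describe immune profiles on TAC-based versus EVR-based immunosuppression, so regimen assignment should not be left to local reading.

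The EVR-intolerance gap bears on who is infused and how closely subjects are followed. Cohorts 2 and 3 plan three subjects each, so one divergent decision is a third of a dose cohort. Section 8.2 calls liver tests the most reliable marker of post-transplant complications, including acute rejection. In Stage 3 a single severe acute rejection or chronic rejection meets the stopping rule (Table 7). Under Section 15.4.1, weeks at risk accrue only while a subject is on the corresponding treatment.

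**Working it through.** The plan has no power or sample-size figure that bears on this. The check sets the passages side by side and converts units and days.

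**1. Units.** 1 μg/dL = 10 μg/L; 1 μg/mL = 1000 μg/L.

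| Target as printed | In μg/L | Divided by the D7 limit of 8 μg/L |
|---|---|---|
| TAC initial 6-8 μg/dL (synopsis) | 60-80 | 7.5 to 10 |
| TAC-based regimen 3-8 μg/dL (synopsis) | 30-80 | 3.75 to 10 |
| TAC with EVR 3-5 μg/dL (synopsis) | 30-50 | 3.75 to 6.25 |
| EVR 6-8 μg/dL (synopsis) | 60-80 | D7 does not apply |
| EVR 6-8 μg/mL (Section 6.1.1) | 6000-8000 | D7 does not apply |
| EVR 6-8 μg/L (Section 6.1.1, same paragraph) | 6-8 | D7 does not apply |

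The synopsis differs from the rest 10-fold, and Section 6.1.1 differs from itself 1000-fold. The synopsis also disagrees with its own Exclusion Criteria D, which are in μg/L.

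The TAC-based target differs in its numbers as well: 3-8 in the synopsis and Section 6.1.2, but 6-8 in Appendix 1, footnote 5. Appendices 2 and 3 print 3-5 without an exception for TAC-based subjects.

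**2. Steroid dates.** Taking week 5 as day 35, the deadlines are day 35, day 44 and up to day 44 + 2 = 46. The spread is 44 − 35 = 9 to 46 − 35 = 11 days.

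Let s be the day steroids stop. If EVR starts strictly after s, the days left in the window are max(0, 44 − max(30, s + 1) + 1). If a same-day start is allowed, replace s + 1 with s.

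| s | EVR after s | EVR same day allowed |
|---|---|---|
| 35 | 9 | 10 |
| 42 | 2 | 3 |
| 43 | 1 | 2 |
| 44 | 0 | 1 |
| 45 | 0 | 0 |
| 46 | 0 | 0 |

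A subject off steroids on day 45 or 46 passes C1 item 6, misses the Section 6.1.4 deadline and has no EVR start date on either reading. The seven C2 criteria (hepatic artery, urine protein, GFR, wound, hemoglobin, neutrophils, platelets) mention neither steroids nor a missed window, so none assigns this subject to the TAC-based regimen. No D criterion bars infusion.

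**3. EVR intolerance.** Section 6.1.2 makes early termination the stated result of TAC intolerance. Section 6.1.1 has no matching sentence for EVR. Section 6.1.3 tells converters to stop MMF and has no provision to restart it. The switch therefore appears only in the rationale text of Section 1.2.4, and Section 7.1 item 2 allows another course.

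Appendix 3 schedules liver tests at T2 to T13, which is 12 visits after the infusion day. Appendix 5 schedules F1 to F3, which is at most 3.

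**The case against.** **Units.** The stray units can be called clerical: most of the protocol, including the infusion criteria, uses μg/L, and an experienced site would probably notice. That stands as mitigation. It does not remove the need to correct a printed drug target.

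**Steroids.** The ± 2 days matches the Screen C visit window in Table 3, and the problem case is a two-day corner that already departs from Section 6.1.4. Appendix 1, footnote 2 equates 5-6 weeks with days 30-44, so fixing week 5 at day 35 is a convention. All of this is fair. It weakens the 9-to-11-day spread but not the day 45-46 gap, which does not use week 5. A site could also treat a subject who misses the window as ineligible for EVR under Section 6.1.2 and leave that subject on TAC and MMF. That is sensible, but the text does not say it.

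**EVR intolerance.** Section 7.1 says may. TAC-based immunosuppression is itself a study regimen, so a subject switched to TAC-MMF has arguably not discontinued, and criteria D8 and D9 apply only to subjects on EVR. This largely succeeds: the texts can be read together.

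The 12-versus-3 comparison counts scheduled visits only. Appendix 5 keeps continuous rejection and adverse-event assessment, with liver tests at any clinically indicated biopsy. Discontinuations are also reported to the DSMB.

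**Conclusion.** The unit and steroid-date conflicts are errors as written. The EVR-intolerance point is a lesser one, an ambiguity that needs a clarifying sentence. The sizes are 10-fold and 1000-fold for units, and two days (45 and 46) on which a subject eligible for conversion has no permitted EVR start. For EVR intolerance, it is 12 versus at most 3 scheduled post-infusion liver-test visits if a subject is moved early after infusion. The documents give no frequency of EVR intolerance or late steroid withdrawal, so the number of subjects affected cannot be estimated.

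A reader might infer three stronger things that the documents do not support:

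- That one section requires infusion while another requires removal of the same EVR-intolerant subject. Section 7.1 is permissive, and only TAC intolerance carries mandatory termination.
- That the sections disagree on the order of steroids and EVR. Sections 6.1.1 and 6.1.4 agree that steroids stop first; only the calendar dates conflict.
- That the day 45-46 subject is removed or cannot be infused. That subject is unconvertible under the dates given, but passes C1 and meets no D exclusion on this account. The gap affects the regimen, not access to infusion.

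It also remains possible that two investigators, each citing the protocol, handle the same EVR-intolerant subject differently.

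**What to change.** - **Targets.** Print every TAC and EVR trough target in one unit. Reconcile the synopsis, Sections 6.1.1 and 6.1.2 and the appendices, including the TAC-based target of 3-8 versus 6-8 and the unqualified 3-5 in Appendices 2 and 3.
- **Steroids.** Reconcile the synopsis, Section 4.3.3 item 6, Sections 6.1.1 and 6.1.4, and Appendix 1 to one steroid-stop deadline compatible with the EVR start window. State whether EVR may start on the day steroids stop, and which regimen applies to a subject who misses the window.
- **EVR intolerance.** Reconcile Sections 1.2.4, 6.1.3 and 7.1 item 2 to state one consequence before infusion and one after it, with the schedule of events that applies to each.

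Which target, date or clinical rule is right is for the sponsor to decide. The cost is clarifying amendment text, with no new procedures or patients.
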